# 4.4 Study Design

This study is a randomized, double-blind, placebo-controlled, 2-period crossover phase 2 study to evaluate the PD effects, safety, tolerability and PK of multiple daily oral doses of TAK-831 in adult patients with schizophrenia.

Approximately 32 adult male and female subjects between ages 18 and 50, inclusive, with a current Diagnostic and Statistical Manual of Mental Disorders, Fifth Edition (DSM-5) diagnosis of schizophrenia who are receiving stable antipsychotic therapy (no increase, no decrease >25% in dose in the preceding 2 months) will be randomized in to the study. Subjects will have a

Subjects with

extrapyramidal signs or symptoms or depressive symptoms will be excluded.

Additional screening assessments include a physical and neurological exam, clinical laboratory and ECG measures, a urine drug screen, and screening for suicidality and depression using the Columbia Suicide Severity Rating Scale (C-SSRS) and the Calgary Depression Scale Score (CDSS), respectively. Assessment of extrapyramidal symptoms will be performed with the Simpson Angus Scale (SAS). The presence of dyskinesias will be assessed with the Abnormal Involuntary Movement Scale (AIMS).

During the pretreatment days (Days -2 and -1), subjects will participate in a baseline assessment with a cognitive battery, EEG/ERP measures, and the EBC.

Effects of up to 2 dose levels of TAK-831 or placebo will be assessed. Each treatment will be administered daily for a period of 8 consecutive days, separated by a 14 to 21 days washout.

The planned dose levels of TAK-831 to be evaluated will be 500 and 50 mg.

The study will consist of 2 treatment periods, and visits to the clinic at the following times: (1) Screening Period (Days -30 to -3) covering full medical, neurological, and psychiatric examinations; (2) Treatment Visits and in patient stays: On Day -2 of Periods 1 and 2, subjects will be admitted to the clinic for 2-night stays; on Day -2 subjects will undergo baseline clinical assessment procedures and cognitive battery assessment. On Day -1, subjects will receive the baseline EEG and EBC assessments. In Period 1, those who continue to meet all eligibility criteria will be randomized via an interactive response technology (IRT) system to 1 of 2 treatment sequences. On Day 1, subjects will undergo predose blood PK/PD samples, first dosing, and postdose blood draws, after which they will be discharged from the clinic to continue dosing at their residence. Subjects will receive double-blind treatment from Days 1 through 8 (inclusive) with completion of efficacy and PK/PD-related assessments on Days 7 and 8 of each treatment period; and (3), a washout period between Treatment Periods 1 and 2 lasting between 14 to 21 days.

Study participants will receive daily study drug dosing until Day 8 of each period. Clinical assessments, laboratory tests and ECG will be repeated after dosing on Days 7 and 8 as per the schedule of events. Upon completion of the first dosing period, subjects will enter a wash-out

period lasting between 14 to 21 days and will then return to the study site to undergo Day -2 procedures for the next dosing period.

Approximately 10 to 14 days after the last dose of study drug in the second dosing period, a follow-up safety assessment will be performed.

In the event of a subject prematurely discontinuing the study during one of the study periods, an Early Termination Visit must be conducted, at which the safety, PK, plasma D- and L-serine assessments corresponding to a Final Visit will be performed. If a subject discontinues the study during the washout period, only the procedures corresponding to the follow-up safety assessment will be performed.

Subjects who drop out before completing 2 treatment periods of the study may be replaced at the discretion of the study sponsor.

Subjects who do not meet symptom or medication stability criteria (or other entry criteria that may be met by the subject at a future time) may be considered for rescreening with the approval of the sponsor or designee.

Subjects who have been screened but have exceeded the 28-day Screening Period may proceed in the study after a discussion with the sponsor/designee to obtain approval and to determine whether any screening procedures should be repeated before admission on Day -2 of Period 1.

#### 5.0 ANALYSIS ENDPOINTS

## **5.1.1** Primary Endpoints

• Average % of conditioned responses during the EBC test at Day 8.

## **5.1.2** Secondary Endpoints

- MMN amplitude at Fz (electroencephalogram [EEG]) at Day 8.
- P300 amplitude at midline parietal electrode (Pz) (EEG) at Day 8.
- ASSR at midline central electrode (Cz) (EEG) at Day 8.
- BACS cognitive battery composite score at Day 7.
- Plasma D-serine and L-serine levels, and plasma D-serine:total serine ratio at Day 8.
- TAK-831 plasma concentrations.

# **5.1.4** Safety Endpoints

- Percentage of subjects who experience at least 1 treatment-emergent adverse event (TEAE).
- Percentage of subjects who meet the markedly abnormal criteria for safety laboratory tests at least once postdose.
- Percentage of subjects who meet the markedly abnormal criteria for vital sign measurements at least once postdose.
- Percentage of subjects who meet the markedly abnormal criteria for safety ECG parameters at least once postdose.
- Percentage of subjects with treatment-emergent suicidal ideation or suicidal behavior as measured using the C-SSRS.

# 6.0 DETERMINATION OF SAMPLE SIZE

Up to approximately 32 subjects will be enrolled into this 2-period crossover study. Initially 16 subjects will be randomized to 1 of 2 sequences comparing the high dose to placebo. Based on the results of an interim analysis, an additional 16 subjects may be randomized as before or to 1 of the 2 sequences comparing the low dose to placebo.

The expected effect size, defined as the ratio between the mean difference between treatment and placebo divided by the standard deviation of this difference, is 0.6 for the primary endpoint. This effect size is a conservative estimate based on data from [1], which showed an effect size of 0.74 for EBC at 24 hours after initiation of treatment with secretin. In this study of a schizophrenic population, subjects on secretin showed a 24% higher rate of correct responses compared to subjects on placebo (70% vs 46%).

The sample sizes of 16 or 32 subjects have been selected to enable Bayesian analyses to inform dose selection and future drug development under the expected effect size as well as other plausible effect sizes.

# 7.0 METHODS OF ANALYSIS AND PRESENTATION

#### 7.1 General Principles

Baseline values are defined as the last observed value before the first dose of study medication within each study period.

All statistical analyses will be conducted using SAS® Version 9.4, or higher.

All confidence intervals, statistical tests, and resulting P-values will be reported as 2-sided and will be assessed at  $\alpha$ =0.10 significance level unless otherwise stated. P-values will be rounded to 3 decimal places prior to assessment of statistical significance.

Means and medians will be presented to 1 more decimal place than the recorded data. The standard deviations (SDs) will be presented to 2 more decimal places than the recorded data. Confidence intervals about a parameter estimate will be presented using the same number of decimal places as the parameter estimate. For transformed and derived data, summary statistics will be presented to appropriate decimal places.

Where appropriate, variables will be summarized descriptively by study visit. For the categorical variables, the count and proportions of each possible value will be tabulated by treatment group. The denominator for the proportion will be based on the number of subjects who provided non-missing responses to the categorical variable. For continuous variables, the number of subjects with non-missing values, mean, median, SD, minimum, and maximum values will be tabulated.

Screen failure subjects will be grouped and listed at the end.

For summaries by treatment sequence, the TAK-831 dose level will be summarized separately if the low dose is used.

# 7.1.1 Study Definitions

# 7.1.2 Definition of Study Days

Study Day 1 is defined as the date on which a subject is administered their first dose of the medication within each study period. Other study days are defined relative to the Study Day 1 with Day 1 being Study Day 1 and Day -1 being the day prior to Study Day 1.

## 7.13 Definition of Study Visit Windows

A windowing convention will be used to determine the analysis value for a given study visit that applies to observed data. For each visit, a window will be defined such that the lower and upper bounds of each window is generally the midpoint between 2 consecutive study visits.

More than 1 result for a parameter may be obtained in a visit window. In such an event, the result with the date closest to the scheduled visit day will be used. In the event of 2 observations equidistant to the scheduled visit day, the later of the observations will be used.

#### 7.1.4 Conventions for Missing Adverse Event Dates

Incomplete adverse event (AE) start dates will be imputed to determine the relationship between the start date and the informed consent date, as well as the start date and the first dose date of a given Period. All references to *first dose* in this section should be understood relative to each treatment Period.

Incomplete AE dates will be presented as they are in the listings.

The following methods will be used to impute incomplete start dates of AEs:

• If only the month and year of the start date are available and the month and year are different than the month and year of the first dose (of double-blind study medication) or the stop date is prior to the first dose, then the first day of the month will be used for the start date. If only

the month and year of the start date are available and the month and year are the same as the month and year of the first dose and the stop date is not prior to the date of first dose, then the date of first dose will be used for the start date.

• If only the year of the start date is available, and the year is different than the year of the first dose or the stop date is prior to the first dose, then January 1st will be used for the start date. If only the year of the start date is available, and the year is the same as the year of the first dose and the stop date is not prior to the date of first dose, then the date of first dose will be used for the start date.

If the above instructions indicate conflicting start dates for an AE, then the earliest date indicated shall be used.

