10.2.8.2 Reporting AEs

At each study visit, the investigator will assess whether any subjective AEs have occurred. A neutral question, such as "How have you been feeling since your last visit?" may be asked. Subjects may report AEs occurring at any other time during the study. Subjects experiencing an SAE prior to the first exposure to investigational product must be monitored until the symptoms subside and any clinically relevant changes in laboratory values have returned to Baseline or there is a satisfactory explanation for the change. Nonserious AEs that begin prior to the first exposure to investigational product, related or unrelated to the study procedure, need not be followed-up for the purposes of the protocol.

All subjects experiencing AEs, whether considered associated with the use of the study medication or not, must be monitored until the symptoms subside and any clinically relevant changes in laboratory values have returned to Baseline or until there is a satisfactory explanation for the

changes observed. All AEs will be documented in the AE page of the eCRF, whether or not the investigator concludes that the event is related to the drug treatment. The following information will be documented for each event:

- Event term
- Start and end date and time.
- Pattern of AE (frequency).
- Severity/Intensity.
- Causality (Investigator's opinion of the causal relationship between the event and administration of study drug[s]).
- Action taken with trial drug.
- Outcome of event.
- Seriousness.

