11.0 STATISTICAL METHODS

11.1 Statistical and Analytical Plans

A statistical analysis plan (SAP) will be prepared and finalized prior to unblinding of treatment assignments to the study team. This document will provide further details regarding the definition of analysis variables and analysis methodology to address all study objectives. In cases of inconsistencies between the protocol and the SAP in regard to data analysis, the SAP is to take precedence over the protocol. Due to this clear understanding of precedence, the statistical analysis section will not necessarily be updated to match the SAP when the protocol is amended.

A targeted data review will be conducted prior to unblinding of treatment assignments to the study team. This review will assess the accuracy and completeness of the study database, subject evaluability, and appropriateness of the planned statistical methods.

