15.1 CRFs (Electronic and Paper)

Completed eCRFs are required for each subject who signs an informed consent.

The Sponsor or its designee will supply investigative sites with access to eCRFs. The Sponsor will make arrangements to train appropriate site staff in the use of the eCRF. These forms are used to transmit the information collected in the performance of this study to the Sponsor and regulatory authorities. eCRFs must be completed in English. Data are transcribed directly onto eCRFs.

After completion of the entry process, computer logic checks will be run to identify items, such as inconsistent dates, missing data, and questionable values. Queries may be issued by Takeda personnel (or designees) and will be answered by the site.

Corrections are recorded in an audit trail that captures the old information, the new information, identification of the person making the correction, the date the correction was made, and the reason for change. Reasons for significant corrections should additionally be included.

The principal investigator must review the eCRFs for completeness and accuracy and must sign and date the appropriate eCRFs as indicated. Furthermore, the investigator must retain full responsibility for the accuracy and authenticity of all data entered on the eCRFs.

After the lock of the clinical study database, any change of, modification of, or addition to the data on the eCRFs should be made by the investigator with use of change and modification records of the eCRFs. The principal investigator must review the data change for completeness and accuracy, and must sign and date.

eCRFs will be reviewed for completeness and acceptability at the study site during periodic visits by study monitors. The Sponsor or its designee will be permitted to review the subject's medical and hospital records pertinent to the study to ensure accuracy of the eCRFs. The completed eCRFs are the sole property of the Sponsor and should not be made available in any form to third parties, except for authorized representatives of appropriate governmental health or regulatory authorities, without written permission of the Sponsor.

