#### 7.11.1 Adverse Events

Verbatim terms will be coded by SOC and PT using MedDRA (version 20.0 or later).

TEAEs will be defined as any sign, symptom, syndrome, or new illness, regardless of relationship to study drug, that occur after the first dose of study drugs. TEAEs with onset occurring within 30 days (onset date – last date of dose  $+1 \le 30$ ) after study drug administration will be included in the summary tables. All AEs will be included in the listings.

TEAEs will be summarized by treatment. TEAE will only be included for the treatment administered in the Period of its start date, unless it increases in intensity in the following Period, in which case will be handled as a new TEAE on the second treatment.

When calculating the frequency and percentage of subjects who reported TEAEs, a subject will be counted only once for each SOC or PT when multiple TEAEs are coded to the same SOC or PT. For the intensity or relatedness summaries, if a subject reports multiple TEAEs coded to the same SOC or PT, the TEAE with maximum intensity or strongest relationship will be included in the summary. An exception to the previous rule is if the TEAE begins in Period 1 but increases in intensity in Period 2, in which case it will be summarized as separate TEAEs.

AEs with missing intensity will be listed as such in the AE listings, however, will be summarized as severe in summary tables. If the relationship of an event is missing, the relationship for the event will be considered to have been related.

In general, AEs will be tabulated at the following levels: overall summary (subjects with at least 1 AE in any dose or regimen), the MedDRA SOC, and the MedDRA PT. The tables will include the number and percentage (N[%]) of subjects. Summary tables that will be generated will include, but may not be limited to:

- Overview of Treatment-Emergent Adverse Events.
- Treatment-Emergent Adverse Events by System Organ Class and Preferred Term, including number of subjects and events.
- Treatment-Emergent Adverse Events by Preferred Term.

- Serious Treatment-Emergent Adverse Events by System Organ Class and Preferred Term, including number of subjects and events.
- Relationship of Treatment-Emergent Adverse Events to Study Drug by System Organ Class and Preferred Term.
- Drug-Related Treatment-Emergent Adverse Events by System Organ Class and Preferred Term
- Drug-Related Treatment-Emergent Adverse Events by Preferred Term.

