- Intensity of Treatment-Emergent Adverse Events by System Organ Class and Preferred Term.
- Pretreatment Adverse Events by System Organ Class and Preferred Term.
- Most Frequent (>5%) Non-Serious Adverse Events by System Organ Class and Preferred Term
- Treatment-Emergent Adverse Events Leading to Study Drug Discontinuation by System Organ Class and Preferred Term.

In addition, subject mappings for the TEAEs by SOC and PT will be generated.

Data listings will be provided for pretreatment AEs, TEAEs, TEAEs leading to study drug discontinuation, liver function abnormalities, serious adverse events (SAEs), and AEs that resulted in death. AEs happened after 31 days post the last dose of the study drug will be listed as well.

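### When an AE start date is incomplete, the earliest-date tie-break in SAP 7.1.4 lets the Period that does not match the AE override a first-dose date that fits it

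*SAP*

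**What the plan says.** SAP 7.1.4 imputes incomplete AE start dates to place them relative to consent and to the first dose of a given Period. References to first dose "should be understood relative to each treatment Period", so each partial date is processed once per Period:

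- **Match.** If the known month and year (or the year alone) equal those of that Period's first dose, and the AE did not stop before that dose, the start becomes the first-dose date.
- **No match.** If the month or year differs, or the AE stopped before that dose, the start becomes the first of the month, or 1 January when only the year is known.
- **Tie-break.** "If the above instructions indicate conflicting start dates for an AE, then the earliest date indicated shall be used".

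SAP 7.11.1 then assigns events by the resulting date: "TEAE will only be included for the treatment administered in the Period of its start date", apart from an AE that worsens in the next Period. Events before dosing go to a separate table, "Pretreatment Adverse Events by System Organ Class and Preferred Term". The percentage of subjects with at least one TEAE is the first safety endpoint in SAP 5.1.4.

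Protocol 10.2.8.2 requires "Start and end date and time" for every AE. Protocol 15.1 says "computer logic checks will be run to identify items, such as inconsistent dates, missing data, and questionable values", with queries to the site. Protocol 11.1 adds a data review before unblinding: "This review will assess the accuracy and completeness of the study database".

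**The concern.** Within one Period the match and no-match branches exclude each other, so two different dates can arise only between Periods. The tie-break therefore acts only when the Periods disagree. In most such cases one Period has returned an informative first-dose date and the other a default, and the default is the earlier one. The matching branch is then cancelled in the situation it was written for, and nothing else in the SAP gives the matching Period priority.

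Two errors follow. A Period 1 AE can become pretreatment and leave the TEAE tables. A Period 2 AE can be dated before its own first dose and leave the Period 2 treatment. In a crossover of active against placebo, the second error can move an event to the other treatment.

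The first error also runs against the SAP's handling of other missing AE information: SAP 7.11.1 summarizes missing intensity as severe and treats missing relationship as related.

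**Working it through.** The documents give no figure for this point, so the check applies the rule as written.

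**Worked example.** First doses are 10 January (Period 1) and 5 February (Period 2). Period 1 Day 8 is 17 January, so the washout is 19 days, within the 14 to 21 allowed.

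| AE as recorded | Period 1 date | Period 2 date | Date kept | Result |
|---|---|---|---|---|
| January, stopped 15 January | 10 Jan (match) | 1 Jan (different month) | 1 Jan | Pretreatment |
| February, stopped 9 February | 1 Feb (different month) | 5 Feb (match) | 1 Feb | Before the Period 2 first dose |

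Equal months do not always help. With first doses on 5 and 28 March, an AE recorded as March that stopped on 10 March gives 5 March for Period 1. It gives 1 March for Period 2, because it stopped before that dose. 1 March is kept and the AE is pretreatment.

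**Enumeration inputs**

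- Dosing lasts 8 days and the washout 14 to 21 days (Protocol 3.0 and 6.1). Period 2 first dose = Period 1 Day 8 + washout, so first doses are 7 + 14 = 21 to 7 + 21 = 28 days apart.
- All 365 Period 1 start dates in a non-leap year, each washout length and each onset day have equal weight.
- The AE stops 2 days after onset, stops 14 days after onset, or is ongoing.
- Assumed: Period 1 runs to the day before the Period 2 first dose, and an imputed date equal to a first dose counts as a TEAE of that Period.

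At these gaps the two first doses fall in different calendar months for 69% (21 days) to 92% (28 days) of start dates, so disagreement between Periods is the usual case.

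**Day missing, true onset on Days 1-8.** Three values are 2-day / 14-day / ongoing; a single value applies to all three.

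| Error | Current rule | Prefer a compatible first dose |
|---|---|---|
| Period 1 AE to pretreatment | 85.2 / 84.8 / 69.0% | 0 / 0 / 0% |
| Period 1 AE to Period 2 | 0% | 0 / 0.4 / 11.5% |
| Period 2 AE to Period 1 | 85.2% | 9.5% |

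**Day missing, true onset through Day 22**

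| Error | Current rule | Prefer a compatible first dose |
|---|---|---|
| Period 1 AE to pretreatment | 61.7 / 53.2 / 46.3% | 0% |
| Period 1 AE to Period 2 | 0% | 1.9 / 26.4 / 34.3% |
| Period 2 AE to Period 1 | 62.2% | 3.5% |

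**Day missing, true onset 1 to 30 days before the first dose.** Counted as a TEAE: 0 / 0 / 1.9% now, 6.3 / 35.2 / 49.1% under the alternative.

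**Year only, true onset on Days 1-8.** Period 1 to pretreatment: 98.8 / 97.3 / 5.8% now, 0% under the alternative. Period 2 to Period 1: 98.8% now, 92.3% under the alternative. Ongoing AEs with onset 1 to 30 days before the first dose count as TEAEs in 89.0% now and 95.8% under the alternative.

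**Sensitivity** (leap year, last dose on Day 9, or one more washout day; day missing, Days 1-8). Under the current rule, ongoing Period 1 AEs go to pretreatment in 68.9 to 72.2%; the 85.2% figures do not change. Under the alternative, Period 2 to Period 1 is 7.2 to 9.6%, and ongoing Period 1 to Period 2 stays at 11.5%.

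**Effect on the endpoint.** One subject who loses an only TEAE on a treatment moves that percentage by 1/16 = 6.25 points, or 1/32 = 3.125 points.

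**The case against.** Four arguments deserve weight.

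1. **The affected group may be empty.** AE dates are mandatory, gaps are queried, and completeness is reviewed before unblinding. Subjects are in the clinic from Day -2 to Day 1 and on Days 7 and 8. The percentages are rates among AEs that may not exist. A reported percentage moves only if such an AE is the subject's sole TEAE on that treatment. The partial date also stays visible in the listings. All of this stands, and it keeps the point minor.

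2. **Charging Period 2 AEs to Period 1 assumes that the washout belongs to Period 1.** The SAP does not say so, and Protocol Table 6.a shows the washout as its own column. Of the 85.2%, 54.2 points are imputed dates in the washout and 85.2 - 54.2 = 31.0 points are on Period 1 dosing days. The destination is therefore conditional. Attribution to Period 1 is the natural reading, because SAP 7.11.1 counts TEAEs for 30 days after dosing. On either reading the AE leaves the Period 2 treatment.

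3. **No systematic bias toward one treatment is shown.** Both sequences are randomized and the trial is double-blind, so errors can run from active to placebo or the reverse. This is correct; the rule misplaces events but has not been shown to hide drug effects.

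4. **The alternative trades errors.** Without knowledge of when an AE was recorded, it counts more true pretreatment AEs as TEAEs and moves some longer Period 1 AEs to Period 2. It barely helps Period 2 AEs when only the year is known. This stands too. The preference rests on the SAP's own matching branch and its conservative handling of other missing AE information, and on adding recording information where it exists.

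**Conclusion.** The concern holds. The tie-break in SAP 7.1.4 defeats the matching branch unless both Periods are compatible or dosing began on the default date itself. It is an error in the rule as written, not an omitted detail.

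Its severity is minor. The rates are high among AEs with incomplete dates, but the number of such AEs is unknown and probably small. The effect is confined to the TEAE and pretreatment AE summaries. The rates rest on start dates spread evenly over the calendar, the stated AE durations, and the washout counting as Period 1. The mechanism itself depends on none of these.

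**What to change.** Replace the tie-break sentence in SAP 7.1.4 with text such as:

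> If the partial date matches the month (or the year, if only the year is known) of at least one Period's first dose and the stop date is not before that first dose, use that first-dose date, taking the earliest if both Periods qualify. Use the first of the month or 1 January only if neither Period qualifies. AEs known to have been recorded before the Period 1 first dose remain pretreatment. AEs known to have been recorded before the Period 2 first dose are imputed against the Period 1 first dose only. In the listings, flag every AE placed by the date rule alone and mark those for which both Periods qualify.

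The flag should cover every AE placed by date alone, because most remaining errors are not cases where both Periods qualify.

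The cost is one short SAP paragraph, the listing flags, and a query on the timing of recording for the few AEs concerned. That query is needed because the AE fields in Protocol 10.2.8.2 do not include when the event was recorded. The schedule in Protocol 3.0 also has a single AE assessment mark on Day 1, so a Day 1 visit alone does not separate predose from postdose. Where recording information cannot be obtained, the residual errors shown above remain, and the flag makes them visible.
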